Overview: The primary goal in this group-level randomized trial is to estimate the difference in effects on outcomes, between intervention arms (e.g., CE condition vs. low-intensity control). To test our main hypotheses (that CEP would be more effective than RS in improving client health outcomes and addressing community priorities for housing and employment, while likely increasing services utilization), we will conduct intent-to-treat, comparative effectiveness analyses using intervention status as the independent variable. We will estimate logistic regression models for indicator variables and loglinear models for counts. Consistent with recommendations for group-level trials, (8) main models will incorporate adjustment for baseline status of dependent variables and covariates: age, sex, ≥ 3 chronic conditions, education, race/ethnicity, family poverty, 12-month alcohol abuse or illicit drug use, 12-month depressive disorder, and community. We will weight data for clients with baseline or six-month data to characteristics of eligible clients. For missing data, we will use item-level ^{155, 168} and wave-level ¹⁶⁹ imputation. Estimates and p-values are calculated using SUDAAN (<http://www.rti.org/sudaan/>) taking into account clustering within programs and weighting. We supplement findings from adjusted models with results from raw data to assess robustness. We will use two-sided tests with $p < .05$ for statistical significance.

We will also explore as an alternative approach multi-level models (also known as hierarchical models or random coefficient models) to account for the multilevel data structure with clients nested within units (agencies or relatively autonomous subdivisions thereof), and repeated measurements nested within clients.¹⁷⁰⁻¹⁷³ For this approach, we will apply two-level models for the cross-sectional data with clients nested within units; and three-level models for the longitudinal data with repeated measurements nested within clients and clients nested within units. To perform multilevel analyses, we will use special software such as the MIXED and GLIMMIX procedures in the SAS System V9, HLM6,¹⁷⁰ MLWin¹⁵⁹, Mplus¹⁷⁴ tailored for these analyses.

Two-level model for cross-sectional data analysis The statistical model for a “cross-sectional” analysis with one observation per client, for example Y =satisfaction at 6 months follow-up, is presented via two regression equations:

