where Y_{mij} denotes the outcome at the m -th occasion for the i -th client nested within the j -th unit, $m=1, \dots, t$, $i=1, \dots, n_j$, $j=1, \dots, J$; T_{mij} denotes time relative to baseline, V_j denotes the intervention indicator, X_{ij} denotes vector of other covariates at individual level, and W_j denotes vector of predictors at the organizational-unit level. Our analysis will be focused on the slope coefficient d_{101} that measures the main effect of treatment on the growth rates. Although clustering effects were nearly absent for most PIC analyses, specification of the covariance structure among the random effects will be modeled allowing for covariance between random intercepts and slopes.¹⁷⁵ Given 3 or more repeated measures on individuals and reasonable smoothness assumptions, we will explore curvilinearity through non-linear terms such as a quadratic term in the Level-1 model, allowing insight into whether changes are greater in the first 6 or subsequent 6 months.

We will also apply multilevel models to clinician data, with clinicians taking on the role of “individuals.”

The primary outcome comparisons will be based on client mental health-related quality of life and an indicator of probable depression (see Table 2). Using the clients’ baseline and 6-month follow-up data, we will evaluate the CE intervention effects on primary mental health outcomes, and community priorities/secondary outcomes of physical activity, homelessness risk factors and employment, indicators of quality of care (use of antidepressant medications and healthcare counseling for depression) and services use in all community services sectors. We will take into account the clustered design for a group-randomized trial. We will treat the intervention condition as the primary predictor in an intent-to-treat framework. For a given outcome variable, we will include the baseline measure for that variable as a covariate along with demographic and baseline variables and stratification variables from the study design for additional adjustment. We will also control for other baseline characteristics and stratification variables. To examine intervention effects using longitudinal data (6 and 12 months), we will add individual-level random effects to account for repeated measurements within individuals and include interactions between time and the intervention indicator variable.

Power for 6-Month Client Outcomes Analyses

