In group-level randomized trials design such as PIC and CPIC, the power analysis is complex because there are many factors that influence power^{176, 177}. For a simple group-level randomized trial, the power of a test such as a t-test in comparing two group means is a function of the cluster size (m), the number of clusters (J), and the intra-class correlation (ICC), the ratio of the between-cluster variability between clusters to the total variability. In our application where cluster is organization unit, we use Kish's method^{176, 177} to adjust the standard errors by the variance inflation factor (VIF) defined as $VIF=1+(m-1)\times ICC$, where ICC is the intra-class correlation at the organization unit level. For analysis of repeated measures, we use an extended formula accounting for inter-temporal correlations within individuals and within units¹⁷⁷. Based on PIC data, outcome analyses on depression care and clinic outcomes have shown that the ICC at the clinic level is either absent or around 0.01, and inter-temporal correlation coefficients within individuals and within units over a 12-month time period are greater than 0.60. PIC provider data shows that ICCs are nearly absent for provider experience and around 0.00-0.05 for knowledge. Taking a conservative approach, we assume that ICC at the unit level ranges from 0.00 to 0.02 for client data and from 0.00 to 0.05 for provider data, and that the inter-temporal correlation is 0.50. In the calculation of power for testing intervention effects from a t-test, we use degrees of freedom equal to (number of clusters – 2) when $ICC>0$, which is conservative for assessing significance, although we also explore setting degrees of freedom equal to $N-2$ (N =total sample size) for the scenario where $ICC=0$ (the optimistic scenario). We also note that regression analyses adjusting for baseline covariates and stratification variables can improve statistical power if covariates explain a substantial portion of the uncertainty.¹⁷⁷ All power analyses are conducted with power of 80% or above as adequate, assuming two-sided tests with significance level 0.05. For client data, we provide detailed power analysis for two primary study variables (appropriate depression care and probable depression).

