Our initial power analyses were based on assumptions about effect sizes derived from prior studies of primary care patients, including ethnic minority patients, and that the main intervention effect would be related to increasing rates of treatments for depression. During the partnered design year, as the community leaders requested inclusion of especially vulnerable populations and services sectors for inclusion expanded, for example to faith-based agencies, senior centers, homeless-serving providers, and prisoner-reentry programs, and outcomes were added such employment, we revisited our estimates of power. First, to accommodate the interest

in employment outcomes we submitted a supplemental grant application which was funded, allowing some expansion in sample. However, even after this point, the focus on homelessness and homeless outcomes emerged in planning. This raised several scientific and operations issues, including that we might have greater attrition than planned, necessitating a larger enrolled sample, and that effect sizes might not be as large as planned, because of the greater difficulty in improving outcomes in complex populations. We therefore decided to assume that we needed approximately an increase in enrolled sample relative to our proposed sample for adequate power under more conventional conditions for fielding quality improvement interventions. These adjustments are given in the Table 3 below, including power for originally proposed sample based on prior primary care studies; power for the analysis of the same sample to address employment; and then based on revised assumptions, prior to any recruitment, to capture smaller effect sizes expected for a more clinically and socially vulnerable sample with potentially higher attrition rates. After the participatory design phase, the final study was designed to have a power of .80 with an alpha of .05 (two-sided) and ICC=.00-.02^{176, 177} to detect group difference of 10% to 11% or higher in comparing two proportions and standardized effects size of .20-.22 or higher in comparing two means. Enrolling 557-600 participants per condition (1114-1200 in total) allowed a retention rate of 65-70% at 6 month follow-up.

Table 4. Minimum detectable effect sizes for main analyses (80% power (alpha=0.05), two-sided test)*			
Note	Analytic sample size at 6 months follow-up	Effect Size†	Point Change§
Original grant	500	0.25-0.27	12.43-13.18%
With 30% expansion	650	0.22-0.24	10.92-11.78%

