Community Engagement and Planning Intervention	4 months of planning followed by 2 day training and follow-up supervision led by research/QI experts supported by written toolkits	Trainings coled by community leaders; follow community specifications; resources to match RS (\$15K/Council); network innovation	Modified 4 months of planning with written plan, coled training, monthly oversight of implementation, network innovations	4 months of capacity building and network development to re-engineer toolkit training as partnered training and innovation
Randomization	Group-randomized at program level (agency site/team)	Develop trust in randomization/explore alternatives	Community forums on Tuskegee legacy and scientific advantages of randomization; Council supplies seed numbers to initiate randomization	Group-randomization implemented with trust-building activities
Outcomes	Risk for depressive disorder, mental health-related quality of life, physical functioning, access and use of services, quality of care	Priority for quality of life, wellness and resilience; good physical functioning and physical activity; think of access broadly to include services in alternative locations; add employment and risk factors for homelessness because of economy	Measures re-prioritized, employment and homelessness, food insecurity, financial problems, eviction added as homelessness risk factors; physical activity added to physical functioning for overall good physical health; resiliency items explored;	Mental health quality of life main outcome; mental wellness, life perceived as organized, poor mental health; employment and work loss days; homelessness risk factors primary for community; services use in diverse sectors
Sampling	Initial: 50 programs and screening of 6000 clients to identify and enroll and complete outcomes on 500	To add employment outcomes, 30% increase in sample size required; homeless sample would reduce expected retention from 80% to 65-70%	Expand expected sample size to achieve power for employment analyses; expand enrollment 20% more due to expected attrition	80-100 programs; with screening to enroll 1200 depressed clients yielding 780 at last follow-up
Analysis Approach	Intent to treat; control for baseline value of outcome and covariates; nonresponse weights; adjust for clustering; impute missing data	Include raw data	Conclusions based on modeled data and raw presented to confirm modeling	Modeling as planned plus raw data presented

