We analyzed dichotomous and count outcomes by using a generalized estimating equation (GEE) framework.¹⁸ Specifically, we fitted logistic regression models for binary outcomes and Poisson models for count data using SAS PROC GENMOD, specifying exchangeable correlation at the program level, with regression adjustment for baseline covariates (age, sex, ≥ 3 chronic conditions, education, race/ethnicity, family poverty, alcohol abuse or use of illicit drugs in the past 12 months, depressive disorder in the past 12 months, and community). We then developed a contrast involving a linear combination of coefficients to test intervention effects at each end point (baseline, 6 months, and 12 months) and tested differences between intervention groups in change from baseline to 6 and 12 months.

The results of analyses of binary outcomes are presented as odds ratios, and the results of Poisson regression analyses of count data are presented as rate ratios. We treated time as a continuous variable and examined the fixed effects for time and intervention, and their interactions. We included quadratic terms (squared effect of time and its interaction with the intervention) which allowed insight into whether changes are greater from baseline to 6 months or subsequent months.

In analyzing continuously scaled MCS-12 as the dependent variable, we used a 3-level, mixed-effect regression model by using SAS PROC MIXED. We accounted for the multilevel data structure with clients nested within pro-grams and repeated measurements nested within clients. To account for the intraclass correlation expected in the data, we specified random effects at the program level and an autoregressive covariance structure within clients to account for within-client correlation over time.

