We conducted sensitivity analyses for alternative representations of time as a continuous or class variable and for alternative weighting approaches. To investigate possible nonignorable effects, we used 2 methods. For continuous measures (such as MCS-12 and number of service visits), we multiplied ignorable-model imputations alternatively by 1.1 and 0.9 to reveal sensitivity to 10% departures from ignorable-model predictions with dichotomized versions of continuous measures (MCS-12 \leq 40) based on the imputed continuous value. For categorical imputations where reference cells were based on an underlying continuous measure (that is, predicted response propensity) including an indicator for any utilization and adjusted Bayesian bootstrap imputations reflecting unit nonresponse at a particular time point, nonignorable imputations for cases in nonboundary reference cells were generated by borrowing values from the reference cell with either the next higher or next lower value of the underlying continuous measure.¹⁹ We also conducted 12-month endpoint analysis controlling baseline with weighting adjustment and presented standardized predictions.^{2, 14}

Analyses for 3-year outcome:

We conducted 3 years endpoint analysis controlling baseline with weighting adjustment (see analysis strategy for 6 months). Given multiple secondary outcomes,¹⁹ we built on the false-discovery-rate (FDR) framework²⁰ as extended by Yekutieli and Benjamini²¹ and used both standard and FDR-adjusted p values (pFDR) in interpreting results across a large number of regression analyses. Results with pFDR $<$.05 are viewed as convincing evidence of a difference, and higher pFDR thresholds are considered as suggestive evidence. We separately calculated pFDR for the two primary outcomes, the community-prioritized outcomes, service use in the health care sector, service use in the social-community sector, medication use, and summary utilization indicators.

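### The lead 12-month analysis models the baseline value as an outcome wave instead of adjusting for it, and does not say whether the endpoint or the change contrast decides

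*Combined protocol and SAP*

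**What the plan says.** **The general rule.** Section 5 (Overview, Aim 2) states that "main models will incorporate adjustment for baseline status of dependent variables and covariates". Table 5 in Section 11 gives control for the baseline value as the initial analysis approach and carries it into the final design. Later in Section 5, in a paragraph that opens with the 6-month comparison, the protocol adds: "For a given outcome variable, we will include the baseline measure for that variable as a covariate".

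**The alternative.** Section 5 also describes multilevel growth-curve models with time measured from baseline and attention on the arm effect on the slope. These are introduced as something to explore, not as the main model.

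**What was done at each wave (Appendix A4).**
- 6 months: endpoint models adjusted for the baseline status of the outcome.
- 3 years: endpoint analysis controlling for baseline. A longitudinal model over all waves is a sensitivity analysis.
- 12 months: the lead analysis is a repeated-measures model in which baseline is one of the outcome waves. The GEE covariate list contains demographic and clinical items and community, but not the baseline value of the outcome. No covariate list is given for the mixed model for continuous MCS-12. The stated purpose of the contrasts is twofold: "test intervention effects at each end point (baseline, 6 months, and 12 months) and tested differences between intervention groups in change from baseline". Change is assessed at both follow-up waves. After the sensitivity analyses comes the sentence "We also conducted 12-month endpoint analysis controlling baseline with weighting adjustment".

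**The concern.** The order used at 3 years is reversed at 12 months without explanation: the all-waves model leads and the baseline-adjusted endpoint analysis follows. Three things are at stake.

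1. **Precision.** A baseline value that was collected, and that predicts the outcome, is not used as a covariate in the main test.
2. **Comparability.** The 6-month and 3-year odds ratios are conditional on the baseline outcome and the 12-month odds ratio is not. Odds ratios are non-collapsible, so these are different quantities even under perfect randomisation.
3. **Pre-specification.** Each outcome has an endpoint contrast and a change contrast at 12 months, with no statement of which one decides. The 12-month text also states no multiplicity adjustment, whereas the 6-month text uses Bonferroni for the two primary outcomes and the 3-year text uses false-discovery-rate p values.

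**Working it through.** **Inputs.** Section 5 gives "two-sided tests with significance level 0.05", 80% power, and a design target of "standardized effects size of .20-.22 or higher in comparing two means". Table 5 gives "80-100 programs; with screening to enroll 1200 depressed clients yielding 780 at last follow-up". The power section assumes an ICC of 0.00-0.02 and an inter-temporal correlation of 0.50, and reports prior-study correlations above 0.60 over 12 months. Neither correlation is specific to MCS-12. Equal arms are assumed.

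**Step 1: reproduce the plan's figure.** The detectable effect is (1.960 + 0.842) × 2 × √(VIF/N).
- N = 780, ICC = 0: 2.802 × 2/√780 = 0.201.
- ICC = 0.02, 80 programs: m = 9.75, VIF = 1.175, giving 0.217.
- ICC = 0.02, 100 programs: m = 7.8, VIF = 1.136, giving 0.214.

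A t reference with programs minus 2 degrees of freedom gives 0.216-0.220 for the last two. The stated 0.20-0.22 is reproduced, without baseline adjustment.

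**Step 2: what the 12-month model estimates.** Time, time squared and their arm interactions give six parameters for six arm-by-wave means. The baseline arm difference is therefore free. With complete data the endpoint contrast is the 12-month difference with no baseline-outcome adjustment.

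**Step 3: variance for a continuous outcome.** In units of the 12-month variance, with baseline-to-12-month correlation ρ: endpoint 1, change 2(1 − ρ), baseline-adjusted 1 − ρ².

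| ρ | Endpoint | Change | Adjusted | Saved vs endpoint | Saved vs change | Saved vs better |
|---|---|---|---|---|---|---|
| 0.3 | 1.00 | 1.40 | 0.91 | 9% | 35% | 9% |
| 0.4 | 1.00 | 1.20 | 0.84 | 16% | 30% | 16% |
| 0.5 | 1.00 | 1.00 | 0.75 | 25% | 25% | 25% |
| 0.6 | 1.00 | 0.80 | 0.64 | 36% | 20% | 20% |
| 0.7 | 1.00 | 0.60 | 0.51 | 49% | 15% | 15% |

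At ρ = 0.50, N = 780 and ICC = 0, the detectable effect falls from 0.201 to 0.201 × √0.75 = 0.174. Power at 0.20 SD rises from 79.8% to 89.7%. With the 733 clients who completed 12 months (364 and 369), power rises from 77.3% to 87.8%.

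**Step 4: missing data.** The table assumes complete data. A likelihood model recovers some information from incomplete records. With an assumed pattern close to the reported counts (1,018 clients; about 980, 760 and 732 at the three waves) and a 12-month correlation of 0.50, the saving is about 19-21%.

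**Step 5: MCS-12 of 40 or less.** Assume 50% positive at both waves and a latent correlation of 0.50. Then φ = (2/π) × arcsin(0.5) = 0.333. On the risk-difference scale the variances are endpoint 1.00, change 2(1 − 0.333) = 1.33, adjusted 1 − 0.111 = 0.89. The saving is 11% against endpoint and 1 − 0.89/1.33 = 33% against change.

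**Step 6: PHQ of 10 or more.** Entry required a PHQ-8 of at least 10 at screening. Appendix A4 counts 995 of 1,018 clients as still at risk of clinical remission at baseline, so about 97.7% were positive. The largest possible φ² with a 12-month rate p is (0.0226/0.9774) × p/(1 − p): 2% at p = 0.50, 4% at 0.65, 9% at 0.80 (p is assumed). Baseline adjustment can save very little here.

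**Step 7: two contrasts.** For a continuous outcome the endpoint and change statistics correlate at √((1 − ρ)/2), which is 0.50 at ρ = 0.50. If significance on either at 0.05 were accepted, the type I error would be about 9.1% per outcome (8.8-9.4% for ρ from 0.3 to 0.7).

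**The case against.** The strongest reply is that the model was foreseen and the adjusted analysis was run. Section 5 describes a growth curve from baseline and a quadratic term to show whether change is greater in the first or second six months. With client waves at 0, 6 and 12 months, that needs baseline as an outcome wave, and the appendix follows the idea closely. Its stated focus on the slope also suggests an interest in change. This stands in part: a reader might infer that the 12-month analysis simply breaks the protocol, and the documents do not support that. They do call the growth curve an alternative to explore, and the main-model rule is baseline adjustment.

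A reader might also infer that no baseline-adjusted 12-month result exists. It does, with weighting and standardized predictions. The question is which analysis leads.

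The magnitude argument has limits that stand. The 25% is the peak loss against the better contrast, and it concerns continuous MCS-12, whereas the primary outcomes are dichotomies. The mixed model's covariates are not listed, so the omission is documented only for the GEE. Covariates such as 12-month depressive disorder may already recover part of the gain. If 0.50 were the correlation between adjacent waves under an autoregressive structure, the 12-month correlation would be 0.25 and the saving against endpoint only 6%. It would be wrong to infer that every 12-month test loses a quarter of its precision.

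Nor is bias shown. Under randomisation the linear endpoint, change and adjusted contrasts target the same mean difference, so the comparability point applies to odds ratios, not to continuous MCS-12.

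Last, the appendix is in the past tense, so promoting another model could itself look like a choice after results. That carries little weight here, because the promoted analysis is the one that the main-model rule already called for.

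**Conclusion.** The point holds as one of precision, comparability of odds ratios across waves, and pre-specification. The lead 12-month analysis does not follow the stated main-model approach or match the 6-month and 3-year main analyses, and it leaves two contrasts per outcome without a deciding one.

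The size depends on the outcome:
- **Continuous MCS-12:** the figures in the Step 3 table apply if the mixed model uses the GEE covariates. No MCS-12 correlation is given, so they are a range and not an estimate.
- **MCS-12 of 40 or less:** a modest gain over endpoint and a larger one over change, resting on the assumed 50% prevalence and latent correlation, and not directly transferable to the odds-ratio scale.
- **PHQ of 10 or more:** negligible.

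The documents do not show that the either-contrast error rate in Step 7 was incurred. They only leave it open.

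**What to change.** Make the baseline-adjusted 12-month arm contrast the main 12-month test, in one of two ways:
- promote the existing 12-month endpoint analysis that controls for baseline; or
- fit 6- and 12-month values as outcomes, with the baseline value of that outcome as a covariate, plus arm, time, arm-by-time and the existing covariates, and name the 12-month arm contrast as the test.

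Keep the all-waves model as a sensitivity analysis, as at 3 years, and label the change-from-baseline contrasts descriptive. State the covariates of the MCS-12 mixed model. Say in the text that the change applies the main-model rule already in Section 5, so that it is not read as a choice made after results.

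Cost: with the first option, SAP wording and order of reporting only. With the second, one rerun on data already held. No new data are needed: 37 of the 1,018 clients have no baseline survey (1,018 − 981), and Appendix A3 already imputes baseline for them.
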